## 8.2 ADDITIONAL EXPLORATORY ANALYSES

### Effect Modification

We will perform additional analyses to explore potential effect modifiers of the LINC-II intervention. The 3 potential effect modifiers of interest are: gender, ever ART, and 30-day IDU. We will fit separate models including 2-way interactions between randomization group and each potential effect modifier. If an interaction is significant, subsequent stratified analyses will be conducted to explore and describe the effect of the LINC-II intervention by categories of the moderator.

### Mediation

Exploratory analyses will be conducted to assess potential mechanisms that may drive LINC-II's ability to improve HIV care outcomes using the Baron and Kenny approach. The 3 potential mediators we will explore are decreases in substance use, HIV stigma, and substance use stigma. However, because the interpretation of the degree of mediation in logistic models is complicated by their inherent nonlinearity, we will conduct additional analyses using the recently developed causal inference approach to mediation (also referred to as the counterfactual framework), an approach that allows potential interactions between the interventions and mediators and derives direct and indirect effects for binary outcomes. We will use the Stata mediation package to conduct these analyses.

### Aim 2

The analyses for this aim will be descriptive in nature; formal hypothesis testing will not be conducted. Descriptive statistics (e.g., means, medians, interquartile ranges, and confidence intervals) will be obtained to assess quantitative data from provider, administrator, and patient surveys over time on perceptions and experiences of coordinated care. We will also conduct repeated measures analyses of

patients' attitudes and experiences using mixed effects regression models controlling for randomized group to assess overall changes over time and to explore and describe potential differences between study arms. Qualitative interview data will be analyzed following a thematic approach. Content analysis of qualitative data will reveal themes regarding care coordination and will identify best practices for LINC-II implementation in similar settings, (e.g., where addiction and HIV care systems are largely separate). Qualitative and quantitative results will be triangulated.

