### 2.3 STUDY OUTCOMES

[figure not shown]
**Aim 1.** The primary outcome for aim 1 is defined as an undetectable HVL at 12 months post randomization, assessed by study test within a window of 9–15 months. Secondary outcomes are initiation of ART within 28 days of randomization, change in CD4 count between baseline and 12 months (assessed by study test), retention in HIV care (at least 1 visit to medical care in 2 consecutive 6 month periods within 12 months of enrollment, assessed by medical record review and by self-report), undetectable HVL at 6 months post randomization assessed by study test, and a composite outcome for achieving both HVL suppression and past 30-day opioid abstinence assessed at 6 and 12 months.

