##### 12 Month (52-week) Visit

- Window open: 271 days post baseline
- Target date: 365 days post baseline
- Window close: 455 days post baseline
- Window length: 184 days

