## 5.2 FOLLOW UP ASSESSMENTS

Content of assessments administered at the 6-, and 12- month visits will be subsets of the baseline assessment (see table below). Phone assessments will be permitted for 6 and 12 month (24 and 52

weeks) assessments, as a last resort, for participants who are unable to come in-person. Questions about COVID-19 will only be asked at one time-point, either the 6- or 12-month assessment.

Administered Assessment	Study Time Point			
	Baseline	Medication Check-Ins	6-Month	12-Month
Demographics	X			X
HIV Testing and HCV Diagnosis	X			X
ART Use and Adherence	X		X	X
Health Care Utilization	X		X	X
Costs of Illness and Treatment in Last Month	X		X	X
Attitudes Toward Care Coordination & Care Continuity	X		X	X
Barriers to Medical Care	X		X	X
Perceived Discrimination in Health Care	X		X	X
DSM-5 Opioid Use Disorder	X			
Drug Use	X		X	X
TLFB: Opioids	X	X	X	X
Tobacco Use	X			
Alcohol Use: AUDIT	X			X
Opportunistic Infections			X	X
Medications	X		X	X
Pain assessment			X	X
HIV Sex Risk Behaviors and Reproductive Health				X
*Sexual Partners	X			X
*HIV Risk Categories	X			
*HIV Disclosure	X		X	
*HIV Stigma	X			X
*Substance Use Stigma	X			X
*Barriers to Medical Care Part 2	X		X	X
*Depressive Symptoms (CES-D)	X			X
*Anxiety (GAD-7)	X			X
*Case Manager Questions			X	X
*Partner Violence and Sexual Assault			X	
Overdose and Suicide			X	X
Social Support Scale	X			
VR-12 Health Survey – MOS-HIV	X			X
Primary Activity	X		X	X
Visit Costs			X	X
COVID-19 Questions			X	X

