#### 5.2.A. MEDICATION VISITS ASSESSMENTS

Medication symptoms and opioid use will be assessed during the medication check-in visits.

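### HIV stigma and substance use stigma are re-measured only at the 12-month visit, so the planned mediation analysis cannot tell an effect of stigma on viral load from an effect of viral load on stigma

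*Combined protocol and SAP*

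**What the plan says.** Section 8.2 (Mediation) plans exploratory analyses of how LINC-II might improve HIV care outcomes, first by Baron-Kenny and then by the counterfactual approach. It names the mediators: "The 3 potential mediators we will explore are decreases in substance use, HIV stigma, and substance use stigma". It gives no measurement time for any mediator, no lag and no check for reverse causation.

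The section 5.2 table marks HIV stigma, and likewise "Substance Use Stigma", at baseline and 12 months only. Section 5.2.A adds no stigma measurement between those visits: "Medication symptoms and opioid use will be assessed during the medication check-in visits". Substance use is followed more closely. The opioid row reads "TLFB: Opioids X X X X", that is, baseline, medication check-ins, 6 and 12 months. The general drug use row is marked at baseline, 6 and 12 months.

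Section 2.3 defines the primary outcome as "undetectable HVL at 12 months post randomization, assessed by study test within a window of 9–15 months". Section 3.6.A puts the 12-month visit at day 271 to day 455 ("Window length: 184 days"). Section 3.7.B allows a viral load already on file at the City AIDS Center within that window to replace a new test.

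**The concern.** A mediation claim needs the mediator to change before the outcome does. Here the only change in stigma that can be computed runs from baseline to the 12-month visit, the visit that also supplies the primary outcome. A participant who has become undetectable may feel less stigmatised as a result. The data would then show an association between stigma and viral load after adjusting for arm, and that is exactly what both planned methods treat as the mediator-outcome path. More data of the same kind would not resolve the direction.

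The stake is the stated purpose of this analysis, which is to identify mechanisms. A false stigma mechanism could shape how the intervention is explained and adapted. The estimate of whether LINC-II works does not depend on it.

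**Working it through.** **1. Timing, from the section 5.2 table and section 3.7.B**

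| Measure | Baseline | Medication check-ins | 6 months | 12 months |
|---|---|---|---|---|
| HIV stigma | yes | no | no | yes |
| Substance use stigma | yes | no | no | yes |
| Drug use | yes | no | yes | yes |
| Opioid use (timeline followback) | yes | yes | yes | yes |
| Viral load | yes | no | yes | yes |

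Neither stigma mediator has a follow-up value before the 12-month visit. If a viral load on file is used, it may predate the questionnaire by up to 455 − 271 = 184 days. Section 8.2 speaks of HIV care outcomes in general. For 28-day ART initiation and 6-month viral load, the stigma measure always follows the outcome.

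**2. The plan's own figure (section 2.8.A)**

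The plan gives no figure for mediation, so I checked the primary-outcome inputs used below: 10% v 27%, 192 evaluable (96 per arm), alpha 0.05 taken as two-sided.
- Without continuity correction: n = [1.96·√(2·0.185·0.815) + 0.842·√(0.10·0.90 + 0.27·0.73)]² / 0.17² ≈ 81 per arm.
- With correction: (81/4)·[1 + √(1 + 4/(81·0.17))]² ≈ 92.4, so 93 per arm.
- At 96 per arm the corrected power is 81.8%, against 80% stated. The inputs are consistent.

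**3. Illustration with true mediation zero**

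There are 96 per arm. The outcome Y is drawn at 10% or 27% by arm A and does not depend on stigma. The decrease in stigma is M = e + d·Y + a·A, with e standard normal. Here d (the reverse effect) and a (the direct arm effect on stigma) are assumptions. Path a is the linear regression of M on A. Path b is the logistic regression of Y on A and M. False mediation means both are significant at 5%. The share mediated is the natural indirect effect divided by the total effect. There were 1,500 trials per setting.

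| d (SD) | Path b alone, a = 0 | Joint, a = 0 | Joint, a = 0.3 | Joint, a = 0.5 | Share mediated, a = 0 / 0.3 / 0.5 |
|---|---|---|---|---|---|
| 0 | 5.2% | 0.1% | 2.5% | 4.5% | about 0 |
| 0.3 | 34.5% | 1.8% | 21.1% | 30.9% | 1.5 / 11.8 / 17.5% |
| 0.5 | 74.9% | 6.3% | 52.2% | 69.9% | 4.4 / 20.1 / 29.9% |
| 0.8 | 98.0% | 13.9% | 81.7% | 97.1% | 11.2 / 33.2 / 46.8% |

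A separate run gave joint rates of about 3/7/14% (a = 0), 22/52/79% (a = 0.3) and 30/71/97% (a = 0.5). Another, of 3,000 trials with a = 0, gave 1.9/6.0/14.7%. The spread is simulation error. Baron-Kenny's opening step, a significant total effect, was not imposed. Imposing it could only lower the rates.

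The a = 0 column is small because the arm then reaches stigma only through Y. The expected arm difference is 0.17·d = 0.051, 0.085 or 0.136 SD, against a standard error of about √(2/96) = 0.144 SD.

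**4. Does a 6-month measure cure it?**

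Assume 70% of those undetectable at 12 months were already so at 6 months, against 5% of the others. A 6-month stigma value affected by 6-month suppression still gives a falsely significant path b in about 18%, 38% and 71% of trials. Adding 6-month viral load to the outcome model returns this to about 5%.

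**The case against.** The strongest reply is that the analysis is labelled exploratory, and that no aim, alpha allocation or sample size rests on it. That stands, and it limits the severity. It does not answer the point, because the analysis exists to suggest mechanisms and timing is what it lacks.

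The reverse effect is also assumed. The documents give no effect of suppression on either scale, and the case is less obvious for substance use stigma than for HIV stigma. That stands too: with d = 0 nothing goes wrong.

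The order is not uniform either. Section 3.7.B allows a repeat blood draw 4 weeks later, or after COVID-19 restrictions lift, so for some participants the questionnaire comes first. This arises by accident of scheduling and gives no usable lag.

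Three stronger readings are tempting and unsupported:
- A reader might take the path-b rates (about 34%, 73% and 98%) as the chance of a false mediation finding. They describe one path only. Both planned methods also need an arm effect on stigma, and without a direct one the joint rate is far lower. The higher rates need the further assumption that LINC-II itself lowers stigma. Naming stigma as a mediator presupposes this, but the documents do not quantify it.
- A reader might conclude that the mechanism question will be answered wrongly. The documents support only that it can be.
- A reader might regard substance use as safe. It is so only if the 6-month value is used. Section 8.2 does not say which value applies, and a 12-month value would have the same weakness.

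**Conclusion.** The point holds as a limited one that should be fixed. The timing is a matter of record: the only follow-up stigma measurement is at the 12-month visit, and neither planned method can recover direction from it. The size is uncertain. With assumed reverse effects of 0.3 to 0.8 SD, false joint significance is about 3% to 14% with no direct arm effect on stigma, and about 22% to 79% with a direct effect of 0.3 SD. It is at most 5% with no reverse effect. These figures rest on the plan's 96 evaluable per arm and 10% v 27%, and on effect sizes that I chose. The primary and secondary comparisons are untouched.

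**What to change.** - **Collection (section 5.2).** Add both stigma scales at the 6-month visit, which already has a self-administered computer component (section 3.3.A, process evaluation table). The 6-month window closes on day 270 and the 12-month window opens on day 271, so an in-window 6-month value precedes an in-window outcome.
- **Analysis (section 8.2, Mediation).** Specify the 6-month value of all three mediators for the 12-month outcome, adjusted for the baseline mediator value, ever ART use and 6-month viral load. State that 6-month viral load is itself affected by arm. The adjusted estimate therefore leaves out any stigma effect already expressed by 6 months, and natural indirect effects need that extra assumption spelled out.
- **Scope.** Do not run stigma mediation for outcomes that precede the stigma measure, such as 28-day ART initiation.
- **If 6-month collection is no longer feasible.** The documents do not give enrolment status. In that case keep 6-month substance use as the only time-ordered mediator, and report 12-month stigma as an arm comparison or association, not as mediation.

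The cost is a few more minutes of questionnaire at one existing visit, or the loss of one exploratory result. If the scales start part-way through the trial, only later participants contribute, and the SAP should say whether that subset is large enough to analyse.

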### **Aim 3**

Aim 3 is to estimate cost and cost-effectiveness. For this analysis, we will adapt methods developed by co-investigator [name] and colleagues in South Africa. When all follow-up to the primary outcome (12-month viral suppression) has been completed, patient resource utilization will be extracted from patients' medical records for HIV care and study forms for narcology care in the intervention arm. Narcology care (number of outpatient visits and services provided) for patients in the control arm will be estimated from patient self-report at the time of 6 and 12-month outcome assessments. Unit costs will be obtained from published information, external suppliers, and the study sites' finance and procurement records and applied to the resource usage data to provide an average cost per study patient. Costs will be measured from the provider perspective and will include the cost of all resources utilized for each study participant from the date of randomization for a period of 12 months, including all drugs, laboratory tests, outpatient visits, case manager costs, and fixed costs such as building space, equipment, and administrative staff. For patients referred to local clinics, rather than the study hospital, for ongoing HIV care after ART initiation and/or for narcology care, fixed costs will be estimated at the facility level for a typical local clinic for each type of care.

We will estimate average cost with 95% confidence intervals to the provider per patient enrolled, per patient initiating ART, and per patient achieving viral suppression by 12 months. We will also estimate total cost per patient achieving the primary outcome, which takes into account all the costs for all the patients but divides by only the number with a successful outcome (i.e., 12-month viral suppression) and thereby links the cost of service delivery to the primary outcome. The cost-effectiveness of the intervention, compared to standard care, will also be estimated as an incremental cost per incremental outcome. The cost and cost-effectiveness results will then be evaluated in the context of existing healthcare budgets, resource availability (e.g., trained case managers) other relevant interventions that have been studied in Eastern Europe, and cost estimates for similar countries to help inform policy makers about the affordability and priority of scaling up the program.

In addition to the provider cost estimates described above, the baseline questionnaire will elicit information about patient costs of seeking care, such as transport fares, lost wages, and substitute labor costs (e.g., for childcare). The average cost to patients by arm and by outcome will be estimated and used both to help explain study results (e.g. there may be an association between patient costs and retention in care) and as a component of the overall economic evaluation.

## 9. STAFF TRAINING

### 9.1 TRAINING OF STUDY STAFF

All study staff will be trained on the study protocol. Training will take place in-person in St. Petersburg and via webinars.

For baseline study activities, staff at CAH will be trained addiction psychiatrists, who have experience administering injectable naltrexone to patients. In-person screening, enrollment, and baseline assessment will be performed by CAH staff who are psychologists who have experience working with this population.

Study staff at PSMU are research addiction physicians and nurses with extensive experience performing pharmacotherapy trials, including trials of implantable naltrexone, and are experienced in the surgical procedure of naltrexone implantation. The staff are trained to assess for adverse medication effects and will follow established protocols for identifying and monitoring any ongoing adverse events.

### 9.2 TRAINING OF INTERVENTIONISTS (CASE MANAGER)

The LINC-II intervention training was led by [name], who has substantial experience conducting behavioral intervention trainings internationally and in engaging HIV-positive PWID in medical care. Over the course of 2 days, [name] trained the interventionists in St. Petersburg, providing them with an overview of the theoretical framework, assessment techniques and the LINC-II intervention; they modeled the intervention delivery to assure the use of a strengths-based approach. As per previous trainings in earlier studies, simultaneous translation was used to allow multiple role-playing sessions to be critiqued. Booster trainings will be conducted annually and as necessary based on findings from quality assurance efforts. These intensive trainings as well as the monitoring and observation for quality assurance are designed to limit potential variability due to individual interventionists.

